#### 5.3.2 **Prohibited Treatments**

The following classes of medications and treatments are prohibited during the study treatment period. If the subject has been taking any of these medications before enrollment, there should be a medication-free period of a minimum of 5 days or 5 half-lives of that medication, whichever is longer, before admission to the unit. In general, subjects who require extensive washouts may not be candidates for participation and those cases should be discussed with the medical monitor.

- Benzodiazepines and barbiturates
- Gabapentin and pregabalin
- Anticonvulsants and mood stabilizers
- All hypnotics and sleep aids (with the exception of low-dose diphenhydramine, doxepin, and trazodone as described above)
- Opioids

- Cannabis
- Electroconvulsive Therapy (ECT), rapid transcranial magnetic stimulation (rTMS), vagal nerve stimulation
- Experimental (including hormonal and herbal) treatments of postpartum depression
- Strong inhibitors and inducers of CYP3A4 (Appendix 1)

#### 6.0 INVESTIGATIONAL PRODUCT

#### 6.1 Identity of Investigational Product

#### 6.1.1 **Ganaxolone IV infusion solution**

Manufacturer: Particle Sciences Inc.

Vehicle: Captisol® containing sterile IV solution

Formulation: IV

Strength: 3 mg/ml solution in a glass vial, which is to be diluted with 0.9% saline for the infusion. For details regarding preparation of the infusion solution please see pharmacy manual.

Route of administration: IV

#### 6.1.2 **Placebo IV control solution**

Placebo name: 0.9% saline physiological sterile IV solution

Formulation: IV solution matching ganaxolone in appearance

Strength: not applicable

Route of administration: IV

#### 6.1.3 Ganaxolone oral capsules

Ganaxolone capsules will be provided in size 00 white/opaque gelatin capsules packaged in HDPE bottles with a foil induction seal and child resistant closure. Each bottle will contain 70 capsules. Each capsule contains 225 mg ganaxolone ( $3\alpha$ -hydroxy- $3\beta$ -methyl- $5\alpha$ -pregnan-20-one), and hydroxypropyl methylcellulose, sucrose, polyethylene glycol 3350, polyethylene glycol 400, sodium lauryl sulfate, sodium benzoate, citric acid anhydrous, sodium methyl paraben, microcrystalline cellulose, 30% Simethicone Emulsion, gelatin capsules, polysorbate 80, and sodium chloride.

#### 6.1.4 **Placebo oral capsules**

Placebo formulation is comprised of sucrose spheres of comparable size to the ganaxolone spray layered spheres encapsulated in a size 00 white/opaque gelatin capsule. The weights of placebo capsules are matched to ganaxolone capsules. The placebo capsules will be provided to the sites in bottles identical to the active drug.

#### 6.2 Administration of Investigational Product(s)

For administration of the IV investigational product (IP; ganaxolone or matching placebo [0.9% saline solution]) the investigator needs to use the Sponsor-approved Captisol®-compatible

intravenous infusion bags and infusion sets which are prepared according to the Pharmacy manual. Any substitutions and deviations from the Pharmacy manual need to be approved by the sponsor.

Ganaxolone or matching placebo capsules (Cohort 6 only) will be administered orally with food. Ganaxolone or matching placebo capsules should be taken  $\pm 15$  minutes of a fatty meal or snack (e.g., fatty yogurt, nuts, avocado) and with 240 mL (8 oz) of water at dinner time.

Subjects will be provided with a diary to capture the details of dose administration and associated food intake throughout the treatment period. Subjects will document the number of capsules taken and whether a fatty meal/snack (e.g., fatty yogurt, nuts, avocado) was consumed  $\pm 15$  minutes of taking the capsules.

# 6.2.1 Interactive Voice/Web Response System (IxRS) Technology for Investigational Product Management

The name and address of the Interactive Voice/Web Response System (IxRS) for this study will be maintained in the Investigator's files at each study site.

Interactive response technology will be used for the following investigational product tasks:

- Randomization
- Communication of treatment assignment to sites
- Supply management
- Inventory management and supply ordering
- Expiration date tracking
- Returns
- Emergency unblinding

#### 6.2.2 Allocation of Subjects to IP

This is a double-blind, placebo-controlled study. The actual IP given to individual subjects is determined by a randomization schedule. prepared by an independent third-party vendor. Within cohorts, subjects will be randomized to ganaxolone or placebo in a 1:1 ratio

Subject numbers are assigned to all subjects as they consent to take part in the study. Within each site (numbered uniquely within a protocol), the subject number is assigned to subjects according to the sequence of presentation for study participation.

The randomization number represents a unique number corresponding to IP kit number allocated to the subject, once eligibility has been determined.

After being randomized a subject will be replaced only if she discontinues prior to receiving IP. The replacement subject will receive the same IP assignment as the replaced subject.

#### 6.2.3 **Dosing**

Subjects entering the study will be randomized to ganaxolone or matching placebo at the Baseline Visit. The goal of Cohorts 1-6 is to determine safety, tolerability, PK and efficacy of the IV formulation (and in Cohort 6, the IV formulation followed by oral formulation) of ganaxolone in PPD subjects administered at a predicted dose regimen mimicking the levels of allopregnanolone at the end of pregnancy, or higher.

Infusion rates for ganaxolone IV will be the same as for placebo IV. Cohort 1

The infusion rate for Cohort 1 will be 4 mg/h (16 ml/h of ganaxolone 0.25 mg/ml solution). The infusion rate (4 mg/ml or 16 ml/h) is maintained constant until + 48 hours when the rate is reduced to 2 mg/h and then stopped at + 60 hours.

The infusion rate of 4 mg/ml is estimated to produce a ganaxolone steady state level of about 52 ng/ml after about 24 hours of infusion.

#### Cohort 2

The infusion rate for Cohort 2 will be 8 mg/h (16 ml/h of ganaxolone 0.5 mg/ml solution). The infusion rate (8 mg/ml or 16 ml/h of ganaxolone 0.5 mg/ml solution) is maintained constant until + 48 hours when the rate is reduced to 4 mg/h (8 ml/h of ganaxolone 0.5 mg/ml solution) and then stopped at + 60 hours.

The infusion rate of 8 mg/h is estimated to produce a ganaxolone steady state level of about 100 ng/ml after about 24 hours of infusion.

#### Cohort 3

For Cohort 3, an initial 12 mg bolus of ganaxolone will be given over 2 minutes, followed by ganaxolone infusion administered at a rate of 12 mg/h (24 ml/h of ganaxolone 0.5 mg/ml solution) for 48 hours. The rate is then reduced to 6 mg/h for the next 12 hours. The infusion is stopped at 60 hours.

#### Cohort 4 and 5

Cohort 4 and 5 are optional and will be utilized only if further dose exploration is warranted. The dosing regimen for Cohort 4 and 5 will be decided based on the results of the Cohorts 1-3 and the recommendation of the DRC. However, no bolus doses higher than 16 mg over 2 minutes will be administered. The cap for the maximum infusion rate in Cohorts 4 and 5 will be 16 mg/h.

#### Cohort 6

For Cohort 6, an initial IV infusion 20 mg/h (40 ml/h of ganaxolone 0.5 mg/ml solution or matching placebo) for 6 hours will be followed by oral dose of 900 mg ganaxolone or matching placebo (4 capsules) at dinner time (Day 1). On subsequent nights (Day 2-28) the subject will take 900 mg of ganaxolone, or matching placebo (4 capsules), at dinner time followed by a 3-day

taper (3, 2, and 1 capsule/s per day, respectively (unless the dose is adjusted as per the instructions from the investigator in which case the taper follows instructions in section 3.4.6).

## 6.2.4 **Dose Adjustments**

Sedation and dizziness are known effects of ganaxolone at higher doses. If a subject experiences excessive sedation or dizziness the investigator may adjust the dosing by stopping the infusion for a minimum of 1 hour or until the effects resolve and then restarting the dosing at half the rate prescribed for the cohort (for Cohorts 1-5). For example, if the rate prescribed for the cohort is 4 mg/h (16 ml/h), the investigator may stop the infusion for 1 hour and then restart the infusion at 2 mg/h (8 ml/h). If the dose is adjusted, this must be recorded in the source documentation and eCRF. Under these circumstances the subject must be monitored closely for recurrence of sedation.

If the subject experiences excessive sedation or dizziness during the administration of the bolus dose, the dosing should be stopped immediately. The investigator should wait for a minimum of 1 hour or until the effects resolve and then starting the infusion at the rate prescribed for the cohort. Under these circumstances the subject must be monitored closely for recurrence of sedation. The dose of the oral medication in Cohort 6 may be adjusted by lowering the dose from 900 mg to 675 mg or 450 mg, or matching placebo at dinner time if the subject experiences adverse effects, such as sedation in the morning. If the dose is adjusted, this must be recorded in the eCRF. Other dosing adjustments may be possible, but they should be discussed with the medical monitor.

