#### 3.4.4 **Cohorts 4 and 5**

Cohorts 4 and 5 are optional and will be utilized only if further dose exploration is warranted. Ganaxolone infusion rate will be decided based on the results from previous cohorts. However, no bolus doses higher than 16 mg over 2 minutes will be administered. The cap for the maximum infusion rate in Cohorts 4 and 5 will be 16 mg/h (not including any ganaxolone given by bolus). Ganaxolone was administered to healthy volunteers in Study 1042-0405 at these dose levels and above without any safety concerns (see below for details). With this maximum bolus and infusion rate the amount of Captisol® infused over 24 hours will not exceed the maximum levels achieved with Carnexiv®, an approved IV carbamazepine product.

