#### 3.4.5 **Cohort 6**

For Cohort 6, the goal of initiation of treatment with IV infusion followed by oral capsules is to maximize the speed of onset of antidepressant activity while providing the convenience of oral dosing for the remainder of the treatment period. Under this IV-oral dosing schedule there may not be a need for a prolonged inpatient observation.

This initial infusion is targeted to provide a fast onset of antidepressant activity by delivery of rapid plasma exposures to ganaxolone. At dinner time of Day 1 the subjects will take their first oral dose of ganaxolone 900 mg or matching placebo (4 capsules). This dose is expected to provide mean  $C_{max}$  plasma concentrations of approximately 250-300 ng/mL and mean steady-state levels between 90 and 150 ng/mL, which may be mildly sedating. In previous studies ganaxolone has been given up to a daily dose of 2000 mg, and at single doses of 1000 mg. Based on the previous experience this dose is expected to be safe.

At subsequent nights (Days 2-28), the target dose is ganaxolone 900 mg or matching placebo (4 capsules) at dinner time followed by a 3-day taper (3, 2, and 1 capsule/s per day, respectively). However, based on the assessment of the investigator the dose may be maintained at 675 mg or 450 mg (or matching placebo) in case of adverse events, such as grogginess in the morning. In the case of 3 capsules per day on day 28 the taper will consist of 2, 2, and 1 capsule/s on days 29, 30, and 31, respectively. In the case of 2 capsules per day on day 28 the taper will consist of 1 capsule on days 29, 30, and 31. If the subject cannot tolerate 450 mg (or matching placebo) per dose the investigator will contact the Medical Monitor to discuss dosing options.

Subjects will be provided with a diary to capture the details of dose administration and associated food intake throughout the treatment period. Subjects will document the number of capsules taken and whether a fatty meal/snack (e.g., fatty yogurt, nuts, avocado) was consumed  $\pm 15$  minutes of taking the capsules.

The mechanism by which ganaxolone is postulated to be efficacious under this dosing regimen is restructuring of sleep architecture. Preclinical studies have shown that allopregnanolone has the capacity to modulate sleep, and disturbed sleep architecture is one of the hallmarks of depression.

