# 6.5 Drug Administration

# 6.5.1 Administration of IV IP (Cohorts 1-6)

The IP will be administered IV via an indwelling catheter inserted in a vein on the arm or hand. The IP should be given as continuous infusion as instructed. If the study drug is stopped temporarily (e.g. catheter change) the infusion may be re-started at the same rate as before. A new infusion bag should be prepared every 24 hours. The catheter should be flushed with saline at the same time when the tubing is changed. The catheter site should be inspected for inflammation at least twice a day. For details please see pharmacy manual.

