# 7.0 STUDY PROCEDURES

This is a Phase 2A, double-blind, placebo-controlled, multiple-dose escalation study consisting of up to 6 cohorts. In Cohorts 1-5 the IV formulation of ganaxolone will be used while in Cohort 6 both IV and oral formulations will be used. Approximately 200 women with PPD 18 to 45 years of age will be screened to randomize approximately 100 subjects across the up to 6 cohorts. Approximately 10-30 subjects will be randomized into each cohort. Randomized subjects will receive ganaxolone or placebo in a 1:1 ratio. In Cohorts 1-5 the treatment is administered intravenously (with or without an initial bolus) over 60 hours. In Cohort 6 the treatment is initiated with a 6-hour intravenous (IV) infusion followed by oral ganaxolone or matching placebo. Additional subjects may be included into these cohorts or additional cohorts may be added, but will not exceed 100 randomized subjects for the study.

The screening period for each cohort will be up to 2 weeks. Following the screening period, there will be a 4-day inpatient treatment phase at a hospital or clinical pharmacology unit for Cohorts 1-5 during which a 60-hour infusion of ganaxolone or placebo will be administered (with or without bolus dosing). The subjects will be discharged from the unit on the morning of Day 4. There will be 2 safety follow-up visits after inpatient discharge on post-treatment Weeks 1 and 4.

[figure not shown]
In Cohort 6, following the screening period, there will be a 1-day inpatient treatment phase at a hospital or clinical pharmacology unit during which a 6-hour infusion of ganaxolone or matching placebo will be administered initially from 9 am to 3 pm ( $\pm$ 1 hour) before oral dosing is started at 7 pm ( $\pm$ 1 hour). The subjects will be admitted on Day 0 and discharged from the unit in the morning of Day 2. The first dose of oral ganaxolone (4 capsules; 900 mg) or matching placebo will be administered at dinner time (around 7 pm) of Day 1, 4 hours after the end of infusion on Day 1. Oral dosing is continued as outpatient on Days 2-28. The dosing regimen during the outpatient phase of Cohort 6 is 900 mg or placebo (4 capsules) at dinner time daily. A 3-day taper will follow at days 29, 30, and 31, as described in Section 3.4.6. There will be 3 safety follow-up visits after the last dose on post-treatment Weeks 1,4, and 6.

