## 7.6.7 Visit 8 (Day +29 ±3 days)

• CTNI to conduct HAMD17 interview

- EPDS
- STAI6
- Assess CGI-I
- Review concomitant medications and therapies
- Collect vital signs (BP, pulse, temperature, pulse oximetry, respiratory rate),
- Collect ECG
- Collect urine sample for urinalysis, drug screen and urine pregnancy test
- Collect safety laboratory tests
- Collect a pharmacokinetic sample
- Measure weight
- Stanford Sleepiness Scale (SSS)
- Conduct CSSRS interview
- Collect AEs
- Dispense study medication with a supply to last through the taper period. Provide the subject with dosing instructions. IP return and accountability.
- Begin 3-day taper (3 capsules on Day 29, 2 capsules on Day30, 1 capsule on Day31, or, if Day 28 dose is other than ganaxolone 900 mg or placebo, follow instructions in section 3.4.6)
- Perform physical examination

# 7.7 Post-treatment Follow-up Period (Days +29 to +71) – Cohort 6

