Start 3-day taper		i la contra c										64	x			.

a Infusion starts at 9 am and ends 6 hours later at 3 pm and is administered at a constant rate of 40 mL/hr.

b Twelve pharmacokinetic samples are collected in Cohort 6:

On Day 1 subjects will have 6 PK samplings: at 1 hour after the end of the 6-hour infusion (i.e., at 4 pm), at 7 pm (just prior to the oral dosing), and at 1, 2, 3, and 4 hours post oral dosing (at 8, 9, 10, and 11 pm) as well at 8 am the following morning (on Day 2) prior to discharge.

A pharmacokinetic sample is also collected on Days 8, 15, 22, 29, and 36 during the study visit.

c All HAMD17 ratings, except the one done at screening, will be conducted by CTNI raters.

 $^{d}$ Q15min health checks are done from the time of start of the infusion to the time of discharge. Pulse oximetry (pO2) must be monitored from the start of the infusion throughout the inpatient period, including during the night when the subject is sleeping. The subject should be awakened if pulse oximetry falls < 91%.

e On Day +1 all efficacy assessments should be conducted first before lab draws, if possible.

f All Day +2 assessments, including PK and neurosteroid levels, are to be done before the subject is discharged from the unit.

The following priority order will be in effect when more than 1 assessment is required at a particular time point: 1) HAMD17 2) CGI-I/CGI-S 3) EPDS 4) STAI6 5) SSS 6) CSSRS 7) vital signs 8) ECG 9) safety labs and neurosteroid level 10) PK sample 11) neurosteroid level 12) urinalysis drug screen and pregnancy test 13) physical examination

All outpatient visits have  $a \pm 3$ -day visit window, except Visits 3 and 5 which have just  $a \pm 1$ -day visit window and Visits 4 and 6 which have  $a \pm 2$ -day visit window.

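### The sedation stop-and-restart rule covers only Cohorts 1-5, so no passage expressly governs the Cohort 6 infusion, the highest continuous rate in the study, and the taper cross-references point to the wrong section

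*Protocol*

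**What the plan says.** **The infusion.** Protocol section 6.2.4 names sedation and dizziness as known effects at higher doses. It lets the investigator stop the infusion for at least an hour or until the effects resolve, "then restarting the dosing at half the rate prescribed for the cohort (for Cohorts 1-5"). A second paragraph covers sedation during a bolus. Section 6.2.3 gives the Cohort 6 regimen, which has no bolus: "For Cohort 6, an initial IV infusion 20 mg/h (40 ml/h of ganaxolone 0.5 mg/ml solution or matching placebo) for 6 hours". Section 3.4.4 says of the optional cohorts: "The cap for the maximum infusion rate in Cohorts 4 and 5 will be 16 mg/h".

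Two other passages reach the Cohort 6 infusion. Section 6.5.1, headed Cohorts 1-6, says that after a temporary stop "the infusion may be re-started at the same rate as before", with a catheter change as the example. Table 2 footnote a, repeated in the SAP's Table 2, says the infusion "is administered at a constant rate of 40 mL/hr".

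**The oral dose.** Section 3.4.5 says "At subsequent nights (Days 2-28), the target dose is ganaxolone 900 mg or matching placebo (4 capsules) at dinner time", and then allows 675 mg or 450 mg if there are adverse events. Section 6.2.4 allows the same reductions without naming days. It closes by saying that other adjustments may be possible and should be discussed with the medical monitor.

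**The taper.** For a subject not on 900 mg at Day 28, section 7.6.7 says to "follow instructions in section 3.4.6". Section 6.2.3 and, twice, section 7.0 cite the same number.

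**The concern.** A rule written for sedation and expressly scoped by cohort leaves out the cohort with the highest continuous rate. The event is foreseeable. Section 3.4.6 reports a few sedation scores of 4 and 3 in the Phase 1 cohorts that included 20 mg/h for 4 hours. The SAP (12.3.1.2) already plans to subtract and list infusion interruptions in Cohort 6. So the plan expects interruptions there without saying how one caused by sedation is handled.

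Section 3.2 makes Cohort 6 the place where the safety of the move from IV to oral treatment is studied. The first oral dose comes on the evening of the infusion, so whether sedation that day bears on that dose is a practical question. A site that turns to 3.4.6 for a reduced-dose taper will not find one there.

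**Working it through.** **1. Rates.** Rate (mg/h) = mL/h × mg/mL, from section 3.1. All four stated rates reproduce.

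| Cohort | mL/h | mg/mL | Computed mg/h | Stated mg/h |
|---|---|---|---|---|
| 1 | 16 | 0.25 | 4 | 4 |
| 2 | 16 | 0.5 | 8 | 8 |
| 3 | 24 | 0.5 | 12 | 12 |
| 6 | 40 | 0.5 | 20 | 20 |

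Cohort 6 against Cohort 3: 20/12 = 1.67. Against the Cohort 4-5 cap: 20/16 = 1.25. The word continuous matters, because the Cohort 3 bolus of 12 mg over 2 minutes runs at 12/(2/60) = 360 mg/h while it lasts.

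**2. Which text governs a Cohort 6 infusion stopped for sedation?**

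| Passage | Reaches Cohort 6? | Addresses sedation? | Gives a restart rule? |
|---|---|---|---|
| 6.2.4, first paragraph | No, Cohorts 1-5 | Yes | Yes |
| 6.2.4, bolus paragraph | No bolus in Cohort 6 | Yes | Yes |
| 6.2.4, last sentence | Yes, no cohort limit | Not specifically | No, refers to the medical monitor |
| 6.5.1 | Yes | No, technical example | Permits the same rate |
| Table 2 footnote a | Yes | No | No, describes the planned schedule |
| 7.8.5.4 (oximetry below 91%) | Yes | Yes, wake and assess | No |

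No row answers yes in all three columns.

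**3. Day 1 oral dose.** Capsules: 4 × 225 = 900 mg, 3 × 225 = 675 mg, 2 × 225 = 450 mg. The reductions in 3.4.5 sit under Days 2-28. Those in 6.2.4 carry no day limit. Both sections give morning symptoms as the example, and on Day 1 no morning falls between the infusion and the evening dose. The two sections can be read either way for Day 1.

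**4. Cross-references.** 3.4.6 is cited for the taper once in 6.2.3, twice in 7.0 and once in 7.6.7, four times in all. Section 3.4.6 contains the Phase 1 dose justification. The reduced-dose taper is in 3.4.5.

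**5. Clock times.** Section 7.0 puts the end of infusion at 3 pm (±1 h) and the oral dose at 7 pm (±1 h), and also "4 hours after the end of infusion on Day 1". If the infusion ends at 4 pm, a dose at 8 pm meets all three statements. If it ends after 4 pm, four hours later is after 8 pm, and they cannot all be met.

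**6. Women affected.** Section 3.1 gives about 10-30 randomised per cohort, 1:1, so 10/2 = 5 to 30/2 = 15 on active drug.

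**The case against.** The best case for leaving the text alone has several parts.

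- The half-rate rule is itself permissive, and its parenthetical may limit only the restart clause, so that stopping is open to any cohort. On that reading the restart in Cohort 6 is still unaddressed.
- The medical-monitor sentence has no cohort limit. Oximetry, 15-minute health checks and investigator withdrawal (4.4.1) also apply, and infusion details are referred to a pharmacy manual that is not available here. These are real safeguards. Apart from the manual, whose content cannot be checked, none is a restart rule. The monitoring and withdrawal provisions also cover Cohorts 1-5, where an explicit rule was still written.
- The 20 mg/h rate is not new to people. Phase 1 gave a 6 mg bolus then 20 mg/h for 4 h, and 30 mg/h for 1 h. Total IV dose is also lower in Cohort 6: 20 × 6 = 120 mg, against 12 + 12 × 48 + 6 × 12 = 660 mg in Cohort 3. The 16 mg/h cap is written for Cohorts 4 and 5 only, so exceeding it is no contradiction.
- No subject had needed a dose adjustment in Cohorts 1 and 2 or among the first 13 in Cohort 3 (1.2.1.4). That stands, but at lower continuous rates.

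Three stronger readings are tempting, and the documents do not support them. A reader might infer that 900 mg is fixed, but 3.4.5, 6.2.4 and 7.6.3 allow 675 or 450 mg. A reader might infer that sites must restart at the same rate after sedation. However, 6.5.1 says may and uses a catheter change as its example, and the Cohort 1 and 2 rates are also described as constant in 6.2.3 although 6.2.4 lets them be adjusted. A reader might infer that delivered dose and PK timing are compromised. However, SAP 12.3.1.2 computes IV dose net of interruptions, and Protocol 7.5.2 already ties the Day 1 PK draws to the end of infusion and the oral dose.

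**Conclusion.** The concern holds as a gap in scope plus a plain referencing error. The rule for sedation during infusion omits Cohort 6, whose continuous rate is 1.67 times the highest other rate specified and 1.25 times the cap for the optional cohorts. No other passage fills the gap expressly. Coverage of the Day 1 oral dose is ambiguous between 3.4.5 and 6.2.4. Four taper references name the wrong section.

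The documents do not show that a particular handling is imposed on Cohort 6, or that the planned analyses fail. They give no expected frequency of pauses, so the number of women affected is bounded only by the 5 to 15 on active drug. The conclusion rests on reading the parenthetical in 6.2.4 as written, and on the pharmacy manual not already containing a Cohort 6 sedation rule. If it does, the protocol need only point to it. The change should be made: it concerns subject safety and costs very little.

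**What to change.** In one amendment or clarification letter:

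1. Reconcile 6.2.4, 6.5.1 and Table 2 footnote a so that one passage expressly governs a Cohort 6 infusion stopped for sedation or dizziness, and separate that case from a technical stop. Carry any change to footnote a into the copy in the SAP.
2. Reconcile 3.4.5 and 6.2.4 on whether the Day 1 oral dose falls under the reduction text.
3. Change the four taper references in 6.2.3, 7.0 (twice) and 7.6.7 from 3.4.6 to 3.4.5.
4. As a minor tidy-up, mark the clock times for the post-infusion PK draw in 7.0 and Table 2 as nominal, with the actual end of infusion taking precedence as in 7.5.2. In 7.0, reconcile the oral dose's clock time with its stated interval for the case where the infusion ends late.

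What the rule for Cohort 6 should be is for the sponsor and investigators to decide. The cost is drafting and the usual review of a protocol change. No visits, procedures or analyses are added.
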